10.2.3 Efficacy Analyses

Annualized bleed rate estimate will be calculated as the number of bleed events occurring 4 weeks after the first dose of fitusiran in this study and until the End of Study visit. Bleed-free duration will be defined as the maximum time intervals between 2 bleeding events and will be analyzed descriptively. Bleed rate reduction and percentage reduction compared with pretreatment will also be calculated.

A weight-adjusted consumption of FVIII or FIX or BPA will be assessed.

Patient-reported QoL will be assessed by descriptive statistics for the EQ-5D-5L questionnaire. Descriptive statistics will be provided for observed values and changes from baseline (ie, Day 1, predose in the current study).

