- Onset period: The onset period is defined as the period of time consisting of the first 28 days: Treatment Day 1 to Treatment Day 28 (of TDR14767(ALN-AT3SC-001) and LTE14762) (see above - definition of “Treatment Day”); this is the period of time during which the AT lowering capacity of fitusiran is increasing but has not yet reached therapeutic levels.
- Efficacy period 1: The efficacy period 1 is defined as Treatment Day 29 to earlier of End of study date before the dose pause or the last fitusiran administration date before the dose pause + 28 days, whichever comes first.
- Treatment period 1: The treatment period 1 is defined to be the onset period plus the efficacy period 1.

The revised dose and regimen:

- Dose adjustment period: The dose adjustment period is defined as the dose re-start Day 1 to the earlier of dose re-start Day 168 or the end of study.
- Efficacy period 2: The efficacy period 2 is defined as the dose re-start Day 169 to the end of study visit
- Treatment period 2: The treatment period 2 is defined to be the dose adjustment period plus the efficacy period 2.

All the analysis periods will exclude the period of following intercurrent events to avoid confounding of treatment effect for the primary efficacy analysis based on On-Treatment Strategy:

Intercurrent events:

I. “Dose interruption periods”:

- a. Gap between TDR14767(ALN-AT3SC-001)/ LTE14762 study >28 days and skips at least two doses in the gap: Exclude events occurring on dates starting from the date of the last dose in 001 +29 days to the date of first dose in LTE14762 +28 days and gap duration >84 days.
- b. Clinical hold/dose pause period during LTE14762 study: Exclude events occurring on dates starting from the date of the last dose before dose interruption +29 days to the date of dose resumption +28 days and on-hold duration > 84 days.
 - Dose hold in 2017: The last dose before dose interruption is defined as the last fitusiran administration before 2017 [REDACTED]. The first dose after dose resumption is defined as the first fitusiran administration after 2017 [REDACTED].
 - Voluntary dose pause in 2020: The last dose before dose interruption is defined as the last fitusiran administration before 2020 [REDACTED]. The first dose after dose resumption is defined as the first fitusiran administration after 2021 [REDACTED].

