6.3.1 Analysis of long-term durability and efficacy

6.3.1.1 Annualized bleeding rate

The ABR efficacy analysis will include all bleeding events occurring in the efficacy period. The ABR will be annualized for each participant using the following formula:

$$\text{Annualized bleeding rate (ABR)} = \frac{\text{total number of bleeding events}}{\text{total number of days in the respective period}} \times 365.25$$

The primary efficacy analysis will consist of the ABR results based on the “on-treatment strategy” during the efficacy period (efficacy period as strictly defined in [Section 6.3](#) above, excluding the periods of intercurrent events). The “on-treatment strategy” analysis will also be performed for the onset period and the treatment period. The “treatment policy strategy” analysis, will be performed for the treatment period only, and will consist of the ABR calculations applied to *all* (treated) bleeds (even including surgery periods), taking place during the analysis period of interest only excluding the gap between TDR14767(ALN-AT3SC-001) and LTE14762 where the bleeds were not collected. ABR will be estimated (with 95% CI) using a negative binomial model adjusted by TDR14767(ALN-AT3SC-001) study baseline ABR. No imputations of missing data will be performed in the ABR analyses. The ABR analysis under the original dose and regimen will be performed for the entire efficacy period 1 and also for the treatment period 1 and onset period (for the “on-treatment strategy”), as well as by year for the treatment period 1 (both on-treatment and treatment policy strategies) in order to demonstrate the durability of the prophylactic maintenance. Model based ABR will be provided when there are at least 3 participants in the group and model converges for by-year analysis. Also, additional analyses will be performed including all bleeds, both “treated” and “untreated”.

ABR under the revised dose and regimen after the dose pause for treated bleeding events and all bleeding events during the dose adjustment period, efficacy period 2 and treatment period 2 based on on-treatment strategy will be analyzed respectively. ABR for treated bleeding events during the treatment period 2 will also be summarized based on on-treatment strategy every 6 months. Similar ABR analysis during treatment period 2 based on treatment policy (ignoring all intercurrent events) will be performed as well.

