6.3.1.2 Bleed-free duration

Bleed-free duration (BFD) for each participant will be calculated as the time interval between 2 protocol-defined treated bleeding events, excluding bleeding events that occur during the intercurrent periods during both of the efficacy periods based on on-treatment strategy respectively. If participant don’t have any bleeding event in each of the efficacy period, the overall duration of the corresponding efficacy period will be the bleed-free duration. ABR and maximum BFD (after 1st significant dose) will be summarized descriptively. A similar calculation

of bleed-free duration considering all bleeding events will be performed for clinical hold or voluntary dose pause analysis described in [Section 6.5](#).

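### Bleed-free duration drops bleeds in intercurrent periods but has no rule for an interval that spans one, so the reported maximum can count off-treatment days as bleed-free

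*SAP*

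**What the plan says.** Protocol 10.2.3 sets the statistic: "Bleed-free duration will be defined as the maximum time intervals between 2 bleeding events and will be analyzed descriptively". SAP 3.2.1 lists time between bleeds as an efficacy endpoint. SAP 6.3.1.2 gives the calculation: "Bleed-free duration (BFD) for each participant will be calculated as the time interval between 2 protocol-defined treated bleeding events, excluding bleeding events that occur" in intercurrent periods, within each efficacy period and under the on-treatment strategy. It then says "ABR and maximum BFD (after 1st significant dose) will be summarized descriptively". A participant with no bleed in an efficacy period is credited with the whole length of that period.

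The general rule in SAP 6.3 concerns time: "All the analysis periods will exclude the period of following intercurrent events to avoid confounding of treatment effect". SAP 6.3.1.1 repeats it for the annualized bleeding rate (ABR), "excluding the periods of intercurrent events". The individual hold rule in 6.3, however, is again an instruction to exclude events, on dates "starting from the date of the last dose before dose interruption +29 days to the date of dose resumption +28 days", and it applies when there is "on-hold duration > 84 days".

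SAP 6.5, under dose interruptions, reports maximum bleed-free duration before and after the interruption separately, as an exploratory analysis.

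**The concern.** An ABR is a count divided by a number of days. Removing a period from the analysis removes both its bleeds and its days, and the ratio stays coherent. Bleed-free duration is a difference between two dates. If both bleeds lie in on-treatment time on either side of a hold, shortening the efficacy period does not shorten that difference. Deleting the bleeds between them lengthens it.

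A programmer who follows 6.3.1.2 as written would drop the bleeds in the window and subtract the earlier retained date from the later one. Off-treatment days, possibly with bleeds in them, would then be credited to fitusiran as protection. Because only each participant's maximum is summarized, these lengthened intervals tend to be the ones selected. Two competent programmers could produce different results from this text, and the literal result favours the drug.

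**Working it through.** **Step 1: which excluded periods can be spanned.**
- *2020 pause:* no. Efficacy period 1 ends at the latest 28 days after the last pre-pause dose, and efficacy period 2 starts on re-start Day 169 (SAP 6.3). No interval within either period crosses the pause.
- *2017 hold, two or more consecutive missed doses, surgery and antithrombin periods:* yes. On-treatment time can exist on both sides within one efficacy period.
- *Parent/extension gap:* yes, for participants whose first dose of at least 20 mg was in the parent study, because efficacy period 1 then starts there (SAP 2.7, 5.2, 6.3). SAP 6.3.1.1 says that bleeds in this gap were not collected, so there are no data to show it was bleed-free.
- *Treatment discontinuation:* no. That exclusion runs to the end of the study, so no retained bleed follows it.

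**Step 2: length of the window.** From last dose + 29 days to resumption + 28 days, counting both ends, is (resumption + 28) − (last dose + 29) + 1 = resumption − last dose. The window is therefore as long as the dosing gap. With a trigger above 84 days, the shortest is about 85 days, if on-hold duration means that gap.

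**Step 3: one participant.** Take a 120-day window (assumed), a retained bleed 20 days before it, several deleted bleeds inside it, and a retained bleed 20 days after it.
- Time kept: 20 + 120 + 20 = 160 days.
- Days subtracted: 20 + 20 = 40 days.
- Cut at the window: two stretches of 20 days.

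**Step 4: effect on the maximum.** The documents give no figure to reproduce, so this is a simulation on assumed inputs. It uses a constant (Poisson) treated-bleed rate over 1,600 days, one window starting at day 450, 40,000 participants per row, and keeps those with at least 2 retained bleeds. Cut stretches run from bleed to bleed or between a bleed and the window edge.

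| Window (days) | Bleeds/year | Spanning interval is the maximum: time kept | Same: days subtracted | Mean maximum: kept / subtracted / cut (days) | Kept vs subtracted | Kept vs cut |
|---|---|---|---|---|---|---|
| 85 | 1 | 50% | 44% | 562 / 522 / 481 | +8% | +17% |
| 85 | 2 | 50% | 38% | 472 / 435 / 396 | +9% | +19% |
| 85 | 4 | 45% | 25% | 326 / 297 / 280 | +10% | +16% |
| 85 | 8 | 48% | 14% | 207 / 183 / 178 | +13% | +16% |
| 150 | 1 | 56% | 46% | 579 / 502 / 457 | +15% | +27% |
| 150 | 2 | 61% | 39% | 501 / 426 / 387 | +18% | +29% |
| 150 | 4 | 66% | 26% | 359 / 292 / 275 | +23% | +31% |
| 150 | 8 | 82% | 15% | 249 / 181 / 176 | +38% | +41% |

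The last two columns are ratios of means minus 1, for example 249/176 − 1 = 41%. Repeat runs move the percentages by about one point, so the ranges are about 45% to 82% for the share, 7% to 38% against subtraction, and 16% to 41% against cutting.

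**Step 5: is subtraction enough?** It removes most of the excess at high bleed rates: at 8 per year, 183 against 178 and 181 against 176 days. At 2 per year with a 150-day window it still leaves 426 against 387 days, or +10%. It joins a stretch before the window to one after it and calls the sum bleed-free, whatever happened in between.

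**The case against.** The strongest reply is that the SAP never says to keep the time. Section 6.3.1.2 ties the measure to the efficacy periods under the on-treatment strategy ("excluding bleeding events that occur during the intercurrent periods during both of the efficacy periods based on on-treatment strategy respectively"), and the general rule in 6.3 takes intercurrent periods out of every analysis period, not only for ABR. On that view the days are already gone and one clarifying sentence is missing. This stands in part: the fault is an absent rule, not an instruction to count off-treatment days. But taking days out of the period does not say how to measure between two dates that both remain in it, and Step 5 shows that subtraction does not fully repair the result.

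A reader might infer three stronger things that the documents do not support:
- That the long 2020 pause inflates the measure. It cannot be spanned.
- That the spanning interval is usually the maximum. The SAP gives only a threshold above 84 days; with an 85-day window the share is 45% to 50%. At 1 to 2 bleeds per year the spanning interval would be the longest in 38% to 46% even with the days subtracted, so not every such maximum is an artefact.
- That the excluded windows were full of bleeds. The documents give no count, and in the parent/extension gap bleeds were not collected.

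Two further points stand. Section 6.5 already plans a split at the 2017 hold, though only as an exploratory analysis. Cutting at a boundary also departs from the protocol's bleed-to-bleed wording, so it is a choice that must be stated.

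**Conclusion.** The concern holds as a missing rule with a predictable direction. As written, 6.3.1.2 lets an interval across the 2017 hold, the parent/extension gap, or a missed-dose, surgery or antithrombin period count excluded days as bleed-free, which biases the maximum upward. Under the assumptions in Step 4 the excess is about 16% to 41% over cut stretches and about 7% to 38% over subtracted intervals. These sizes depend on the assumed window, follow-up and constant rate; the documents fix none of them.

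Reach is limited. Only participants with a retained bleed on both sides of an excluded period are affected, plus those with no bleed if the period credited to them is taken gross of excluded time. The endpoint is descriptive with no test, and the primary ABR analysis has its own stated time rule. The SAP should be corrected before the analysis, but the main efficacy result does not depend on it.

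**What to change.** Add to SAP 6.3.1.2:
- A bleed-free stretch ends at the start of an intercurrent period, and a new one starts when on-treatment time resumes. This should cover at least the 2017 hold, the parent/extension gap and missed-dose periods.
- The reported statistic is each participant's longest on-treatment stretch, with stretches cut by an intercurrent period flagged.
- The duration credited to a participant with no bleed in an efficacy period follows the same rule.

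This brings the endpoint analysis into line with the before/after split in 6.5. The cost is a short addition to the SAP and a small programming change. The reported maximum becomes somewhat shorter, and some stretches will end at a boundary rather than at a bleed, which is why they need the flag.

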6.3.2 Quality of life

Descriptive summary for QoL questionnaires will be provided before and after the 2020 voluntary dose pause respectively.

6.3.2.1 EQ-5D-5L

The EQ-5D-5L is a standardized instrument for use as a measure of QoL outcome. Index values and visual analogue scale (VAS) scores and their changes from Treatment baseline to each post-baseline visit will be summarized descriptively. Numbers and percentages of participant by level and dichotomized level (1 = “no problems”, 2 to 5 = “some problems”) of each dimension will be reported.

6.3.2.2 Haem-A-QoL

The Haem-A-QoL includes 46 items contributing to 10 QoL domains (physical health, feelings, view of yourself, sports and leisure, work and school, dealing with hemophilia, treatment, future, family planning, partnership and sexuality). Scoring for each item is based on a 5-point Likert scale (never, rarely, sometimes, often, and all the time), and higher scores represent greater impairment. Total score, domain scores, standardized scale scores, and transformed scale scores and their changes from treatment baseline to each post-baseline visit will be summarized descriptively.

6.3.3 Annualized weight-adjusted consumption of BPA and factor

Weight-adjusted factor/BPA usage will be calculated programmatically. Number of factor or BPA injections per bleed, weight adjusted total dose per injection and total dose per bleed will be summarized descriptively. Additional summary will be provided by bleed location, causality and severity.

6.4 PHARMACODYNAMIC ANALYSIS

Pharmacodynamic analyses before the dose pause will be conducted using the PD analysis set 1. AT activity, AT lowering (% reduction from Treatment baseline) and peak thrombin values will be summarized at each post-baseline visit descriptively. The baseline under the original dose and regimen will be the last non-missing assessment before the first significant dose. Only evaluable PD result will be included in the analysis. The criteria listed in the [Table 3](#).

Table 3 - PD assessment evaluable criteria

Criteria description	AT	TG
Criteria 1 Assessments collected during any of the dose interruption period ^a will be excluded.	X	X
Criteria 2 Assessments collected during the antithrombin treatment ^b period or within 5 half-lives after the antithrombin treatment administration will be excluded.	X	X
Criteria 3 Assessments collected within 48 hours of factor, BPA or antifibrinolytic administration will be excluded.	X	
Criteria 4 Assessment collected at one visit without AUC assessment available on the same visit will be excluded.	X	

a Refers to section 6.3 intercurrent event definition.

b The antithrombin treatment includes Heparin, Antithrombin Concentrate and Factor Xa inhibitors. All the other antithrombin treatment will be adjudicated by Sanofi medical team.

Similar pharmacodynamic analyses after the 2020 voluntary dose pause will be performed based on the PD analysis set 2 by treatment sequence specified in [Section 5.2](#).

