1.5 DOSE RATIONALE

Patients enrolled in this study were initially administered subcutaneous (SC) fitusiran once every month where 1 month has been defined as 30 days to aid in patient compliance with the long-term dosing regimen. Patients started the study on weight-based doses then transitioned early on to a 50 mg- or 80 mg-fixed monthly dose depending on what they received in the parent study.

A once-monthly dosing regimen is supported by preliminary results from clinical and nonclinical studies. Data from the parent study (ALN-AT3SC-001) suggest that a reduction in AT levels is sustained for up to 60 days following a single dose of fitusiran. Additionally, preliminary data in nonhuman primates suggest that steady-state AT suppression can be achieved and maintained after monthly doses of fitusiran.

A change in the fitusiran dosing regimen has been introduced as a risk mitigation measure for vascular thrombotic events in Protocol Amendment 07. As the risk of vascular thrombotic events is thought to be increased in the setting of low AT activity levels, a reduced dose of 50 mg administered SC once every 2 months has been selected to minimize the occurrence of AT activity levels below 10%. At a reduced dose of 50 mg every 2 months, if a patient has more than 1 AT level <15%, the patient will be required to permanently discontinue fitusiran. Patients previously exposed to fitusiran at a dose of 50 mg monthly or 80 mg monthly with no more than 1 AT activity level <15% at any time during fitusiran treatment (based on at least 3 months of prior AT measurements) may have the option to remain on either dose, respectively.

If a patient receiving fitusiran 50 mg once every 2 months has 2 steady state AT levels above 35%, the patient will be dose escalated to fitusiran 50 mg monthly. In very rare cases, if a patient still has 2 steady state AT levels above 35% at the 50 mg monthly dose, the patient will escalate to the 80 mg monthly dose. Details are described in Section 6.5.1.3.

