3 INVESTIGATIONAL PLAN

3.1 OVERALL STUDY DESIGN

This is a Phase 1/2 multicenter, multinational, open-label extension study, conducted at up to 30 clinical study centers worldwide, to evaluate the long-term safety and efficacy of fitusiran in male patients with moderate or severe hemophilia A or B, who previously tolerated dosing in Part B, Part C or Part D of the parent study, ALN-AT3SC-001.

Patients from Part B may roll over into this study after completing Day 70 in the parent study. Patients from Parts C and D are expected to roll over into this study approximately 1 month after completing the 3 monthly doses of study drug in the parent study, thereby maintaining their monthly dosing schedule.

Screening will occur between Day -60 and Day -1. Eligibility for this study will be confirmed before administration of the first dose of study drug. Administrations of fitusiran will occur at the clinical study center or may be self-administered at home under the conditions described below. Patients will be monitored for 6 hours postdose for the first dose only.

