5.2 GENERAL METHODS

Both efficacy and safety analysis under the original and revised dose regimens will be analyzed separately, unless otherwise specified. The data collected during the 2020 voluntary dose pause will be analyzed along with the pre-pause data.

A significant dose is defined as any single dose of fitusiran that is greater than or equal to 20 mg. Before the voluntary dose pause, the analysis period for efficacy endpoints starts from the date of first significant dose up to the earlier of 2020 voluntary dose pause date or the last day of study follow-up. For safety endpoints, the analysis will be performed based on LTE14762 study period data only up until the dose restart date. Date of first significant dose in the TDR14767(ALN-AT3SC-001) and LTE14762 study/studies will be designated as Treatment Day 1; there will be no Treatment Day 0. Participants who receive doses (either weight-dependent or weight-independent) of at least 20 mg but less than 75 mg will be “classified” as “50 mg” participants, while participants receiving doses of greater than or equal to 75 mg will be “classified” as “80 mg” participants (except PK analysis in which actual dose on Day of PK sample collection will be used). However, for purposes of efficacy and safety analyses and summaries in the final CSR report for the LTE14762 study, the classification of each participant under the original dose and regimen will be according to the fixed dose to which they are eventually taken by the end of the LTE14762 study original dose period. For example, participants who received a 50 mg dose in TDR14767(ALN-AT3SC-001) or LTE14762 and then were switched to 80 mg dose at some point in time during the LTE14762 study, are classified in the LTE14762 study as “80 mg” participants (except for PK analyses). Treatment after the volunteer dose pause will be treated as each participant’s treatment sequence.

[figure not shown]
Treatment Days under the original dose and regimen will be calculated as evaluation date – first significant dose date +1 and pre-treatment days will be calculated as evaluation date – first significant dose date. (The pre-treatment day formula applies when evaluation date < first significant dose date; ie, for example, there will be pre-treatment Days ... -3, -2, -1, then treatment Day 1, 2, 3, 4, ...; there is no “pre-Treatment Day 0” nor is there any “Treatment Day 0”).

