5.10 DERIVED ANALYSIS VISIT WINDOWS

For LTE14762 by-visit analyses under the original dose and regimen such as lab and vital sign parameters, it is expected that all 002 study visits will occur according to the protocol schedule of assessments. Analysis visits will be assigned based on LTE14762 evaluation visits as recorded on the CRF even if the assessment is outside of the window for that study visit.

For TDR14767(ALN-AT3SC-001)/ LTE14762 combined by-visit analyses under the original dose and regimen such as PD and QoL endpoints, analysis visits will be defined as follows.

For participants whose first “significant” dose of fitusiran was administered in TDR14767(ALN-AT3SC-001) (eg, this could only occur in the MD cohort [Part C and Part D]; other cohorts are administered relatively small doses of fitusiran),

- a) Analysis visits for all TDR14767(ALN-AT3SC-001) assessments will be first assigned based on TDR14767(ALN-AT3SC-001) evaluation visit as recorded on the CRF and will be adjusted, if necessary, so that the window of the TDR14767(ALN-AT3SC-001) assessment overlaps as much as possible with the LTE14762 scheduling.
- b) Analysis visits will be derived for the LTE14762 Day 1 assessment based on the Treatment Days and will be assigned for subsequent visits based on LTE14762 evaluation visit as recorded on the CRF. For example, Haem-A-Qol is assessed quarterly in the 1st two years and then yearly after in LTE14762. If the Treatment Days for Day 1 visit is within 18 months +/-1.5 month, then analysis visit for Day 1 visit

will be derived as Month 18, and the subsequent analysis visits will be assigned quarterly or yearly after Month 18 accordingly.

For participants whose first “significant” dose of fitusiran was administered in LTE14762, Analysis visits under the original dose and regimen will be assigned based on LTE14762 evaluation visit as recorded on the CRF.

For LTE14762 by-visit analyses under the revised dose and regimen, analysis visits for scheduled visits will be defined based on CRF reported VISIT, even if the assessment is outside of the window for that study visit.

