6.4.1 AT lowering and peak thrombin

Correlation between AT (actual AT activity and AT lowering) and peak TG will be computed on paired assessments, where both parameters are measured on the same day. Log transformation may be used.

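### Percent AT lowering in SAP 6.4 is measured from the last value before the first dose of at least 20 mg, so participants given only smaller doses first can have an on-drug baseline

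*SAP*

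**What the plan says.** SAP 6.4 summarises AT activity, AT lowering (percent reduction from baseline) and peak thrombin by visit. For the baseline it says: "The baseline under the original dose and regimen will be the last non-missing assessment before the first significant dose". SAP 5.2 gives the threshold: "A significant dose is defined as any single dose of fitusiran that is greater than or equal to 20 mg". SAP 5.5 uses the same anchor for all efficacy by-visit analyses and carries it into the revised regimen as the main analysis. The additional restart baseline there is for selected safety endpoints only, and SAP 6.4 plans similar analyses after the 2020 pause without naming another baseline.

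SAP 6.4.1 adds: "Correlation between AT (actual AT activity and AT lowering) and peak TG will be computed on paired assessments".

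On earlier exposure, SAP 6.8.2 notes that all participants were dosed in the parent study. SAP 5.10 says of a first significant dose in that study: "this could only occur in the MD cohort [Part C and Part D]; other cohorts are administered relatively small doses of fitusiran". Protocol 3.1 says of Part B: "Patients from Part B may roll over into this study after completing Day 70 in the parent study". It says Parts C and D are "expected to roll over into this study approximately 1 month after completing the 3 monthly doses of study drug".

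**The concern.** Percent lowering means what a reader expects only if its denominator is an untreated value. The SAP's rule requires that no dose of 20 mg or more came first; it does not require that no fitusiran came first. Doses below 20 mg are not inert: Protocol 1.3.3 reports a 70% mean maximum AT reduction after three monthly doses of 0.225 mg/kg. If such a participant's AT had not recovered when the baseline sample was taken, the denominator is too small and the reported lowering too small.

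Characterising AT reduction is a secondary objective. The error would run in one direction in the by-visit summaries. In SAP 6.4.1 it would put two kinds of denominator into one correlation, with an effect on the coefficient whose direction cannot be told in advance. SAP 2.7 explains the 20 mg anchor for the bleeding analysis periods, on the ground that prior exposure may matter, but does not discuss the pharmacodynamic baseline.

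**Working it through.** The plan states no figure to reproduce; the study is descriptive. The check has three steps.

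**1. Who can have a post-exposure baseline**

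- *Part B roll-overs.* By SAP 5.10 they had no significant dose in the parent study. Their number, doses, time since last dose and AT recovery are not stated.
- *Part C at 0.225 mg/kg (N=3, Protocol 1.3.3).* The weight below which this dose is under 20 mg is 20 / 0.225 = 88.9 kg; at 70 kg the dose is 0.225 × 70 = 15.75 mg. For the next dose, 0.45 mg/kg, the weight is 20 / 0.45 = 44.4 kg. The realistic ceiling is therefore 3 patients. Their weights are not given.
- *Anyone who started the extension below 20 mg with no earlier significant dose.* Protocol 1.5 says "Patients started the study on weight-based doses then transitioned early on to a 50 mg- or 80 mg-fixed monthly dose", and Protocol 6.5 expects a 0.225 mg/kg start. SAP 2.1 has everyone start at 50 or 80 mg. These passages conflict and must be reconciled; until then this group may or may not exist.

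**2. Whether AT could still be suppressed**

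Protocol 1.5 reports that "a reduction in AT levels is sustained for up to 60 days following a single dose of fitusiran" and defines a month as 30 days. Part C patients are expected to enter about 30 days after their third dose, inside that period. Part B patients enter after Day 70 of the parent study, but the interval from their last dose is not given.

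SAP Table 3, Criterion 1, drops pharmacodynamic values collected in a dose interruption. Under SAP 6.3 this includes parent-to-extension gaps of more than 84 days, from 29 days after the last parent dose. The SAP does not say whether the criterion applies to baseline values. If it does, the most recovered values are discarded and the baseline moves back to within 28 days of the last parent dose.

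**3. Size, as an illustration**

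Let T be true lowering from an untreated value and s the residual suppression at the SAP baseline. Then

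reported lowering = 1 − (1 − T) / (1 − s).

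Inputs from Protocol 1.3.3 are mean maximal reductions in this study of 83.6% (50 mg, N=13) and 85.9% (80 mg, N=21). Pooled T = (13 × 83.6 + 21 × 85.9) / 34 = 85.02%. Assumptions: these figures are relative to an untreated value and stand in for by-visit lowering; s lies between 25% (assumed) and 70% (the peak effect of 0.225 mg/kg, entirely unrecovered); 3 participants are affected.

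| Residual suppression s | Reported for one affected participant | Pooled mean, 3 of 34 affected |
|---|---|---|
| 0% | 85.0% | 85.0% |
| 25% | 1 − 0.1498/0.75 = 80.0% | (31 × 85.02 + 3 × 80.03)/34 = 84.6% |
| 70% | 1 − 0.1498/0.30 = 50.1% | (31 × 85.02 + 3 × 50.07)/34 = 81.9% |

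Each further affected participant lowers the pooled mean by (85.02 − 80.03)/34 = 0.15 points, up to (85.02 − 50.07)/34 = 1.03 points.

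**The case against.** Four counter-arguments carry weight.

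First, percent lowering is not a listed endpoint. SAP 3.2.3 lists AT activity and thrombin generation over time, neither of which depends on a baseline, and SAP 6.4.1 also correlates actual AT activity with peak thrombin. This stands and limits the consequence.

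Second, SAP 6.11 already separates participants whose significant dose was in the parent study, who are largely those with a pre-exposure baseline. This stands in part: the subgroup covers AT activity and thrombin generation under the original regimen, but not percent lowering, where the problem lies.

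Third, Protocol 10.2.3 gives a baseline of Day 1 predose in the current study (stated for quality of life), and Protocol 10.2.4 names no other for pharmacodynamics. Read across, that would be post-exposure for everyone, so the SAP is an improvement for participants with an earlier significant dose. True, but it leaves the others as they were.

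Fourth, residual suppression is not shown for any group. The 60-day statement is a maximum with no dose attached, and the SAP foresees long gaps: SAP 6.3 has a rule for those over 84 days, and the example in SAP 5.10 puts extension Day 1 at Month 18. This is why the point is conditional. Long gaps do not settle it, because of the open question over Table 3, Criterion 1.

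A reader might infer that the 50 mg mean could fall from 83.6% to 74.8%. That comes from (10 × 83.6 + 3 × 45.3)/13, where 45.3% = 1 − 0.164/0.30. It puts all 3 patients in the 13-patient group and treats a peak effect as residual suppression. Nothing in the documents supports the first step, and the second is an extreme.

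**Conclusion.** The rule as written allows an on-drug denominator for percent AT lowering. On the protocol's own figures this is plausible for up to 3 Part C patients and possible for an unstated number of Part B roll-overs. If AT was still suppressed, SAP 6.4 understates lowering and SAP 6.4.1 mixes baselines. The documents do not establish that this happened, or how often.

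With 3 of 34 affected, the pooled mean falls by about 0.4 points at 25% residual suppression and about 3.1 points at the 70% extreme; an affected individual falls by 5.0 to 35.0 points. These figures rest on mean maximal reductions from an August 2017 data cut and on an assumed range for s, so they indicate size only. If Part B contributes participants, 3 is not a ceiling.

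A reader might conclude that the study's AT results in general are biased. The documents do not support that: AT activity and peak thrombin values are untouched, and the study is descriptive. The severity is minor.

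**What to change.** - In SAP 6.4 and 6.4.1, for both regimens, calculate percent AT lowering from the last non-missing AT value before the first fitusiran dose of any size in the parent study. Where that value is missing, fall back on the current SAP baseline and flag the participant.
- Keep the current baseline as a sensitivity analysis.
- Report how many participants differ between the two definitions, and for each the days from the last dose below 20 mg to the current SAP baseline. If nobody differs, the count settles the matter.
- State whether Table 3, Criterion 1, applies to baseline values.
- Reconcile SAP 2.1 with Protocol 1.5 and 6.5 on the starting dose, so that the third group can be identified.

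The cost is some SAP wording and a merge of parent-study pre-dose AT values. SAP 6.9 already uses a reference before the first parent-study dose for antidrug antibodies. The drawback is that some participants may lack a pre-parent-dose AT value, hence the flagged fallback.
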